# PPD

Summary statistics of blood glucose level (mg/dL) will be provided by treatment arm at each time point for patients reporting severe hypoglycemia. Derivation of patients reporting severe hypoglycemia will be the same as the one described in 7.2.1.6 section, except that in this case events happened between month 12 and month 18 will be considered as well.

## 7.2.1.9 Average (previous 3 days) daily insulin requirement (IU/kg/day)

Average daily insulin requirement (CRF - INSULIN REQUIREMENT form) and its change from baseline will be summarized at each available timepoint and comparison between treatments will be performed by means of two-sample t-test or, if assumptions of normality are not confirmed (by Kolmogorov-Smirnov test), two-sample Mann-Whitney U test.

## 7.2.1.10 Estimated Glucose Disposal Rate

eGDR comparison between treatments will be performed by means of two-sample t-test or, if assumptions of normality are not confirmed (by Kolmogorov-Smirnov test), two-sample Mann-Whitney U test.

Summary statistics by treatment will be provided along with summary of the change from baseline at each time point for the eGDR-related parameters:

- Weight (Kg) and Height (cm),
- BMI (Kg/m^2) – derived from CRF,
- Waist circumference (cm) and Waist-to-Hip Ratio,
- Hypertension status (Yes, No).

## 7.3 MMTT over the study

Summary statistics of C-peptide (nmol/L) during MMTT will be provided by treatment at each visit and time-interval (Basal1, Basal2, Average Basal, @15min, @30min, @60min, @90min, and @120min after the meal). In addition, for each visit, the following parameters will be summarized:

- C-peptide 0-120 min AUC (nmol/L)
- C-peptide 15-120 min AUC (nmol/L)
- C-peptide Cmax (nmol/L)
- C-peptide Tmax (min)

Individual plots of the Cmax and Tmax means ( $\pm$ SEs) will be presented. Based on the observed trends, additional ad-hoc analyses might be performed.

Derivation rules are reported in Table 3.

## 7.4 Analysis of CCI

[figure not shown]
CCI will be analyzed at each available time points by means of descriptive statistics. Specifically, analyses will be provided for CCI . Comparison between treatments

# PPD

will be performed by means of CCI [REDACTED] or, if assumptions of normality is not confirmed CCI [REDACTED]

Where applicable the investigator's interpretation (Normal, Abnormal NCS, Abnormal NC, No Result) will be summarized and compared by means of a CCI [REDACTED] or, if more appropriate, a CCI [REDACTED] at each time point CCI [REDACTED] will not be considered for the comparison).

The following results will be displayed graphically:

## 8. Evaluation of Safety

### 8.1 Adverse events

Any AE which starts at or after the first administration of study treatment will be considered a Treatment Emergent Adverse Event (TEAE). Pre-treatment AEs and TEAEs will be presented separately. Pre-treatment AEs will be presented in the listings only. In case of missing or incomplete dates not allowing a direct allocation to any of the two categories of AEs, a worst-case allocation will be done according to the available parts of the onset and the end dates (see Table 5). The AE will be allocated to the first category allowed by the available data, according to the following order:

- TEAE;
- Pre-treatment AE.

In case of TEAE, the event can be classified as:

- On Treatment Period, or
- On Follow-up period

according to the available parts of the onset and the end dates (see Table 5).

All AEs will be assigned to a Preferred Term (PT) and will be classified by primary System Organ Class (SOC) according to the MedDRA thesaurus. In addition, each AE will be graded according to severity definitions as "Mild", "Moderate" or "Severe".

TEAEs summaries will be presented, displaying frequencies and percentages of patients reporting AEs. In the summaries, primary SOC will be presented alphabetically and the PT will be sorted within SOC in descending overall frequencies .

Along with AEs, number of events will be reported. On each of these summaries, patients will be counted only once per SOC and, within each SOC, patients will be counted only once per PT.

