### 8.3. RECORDING

AE data should be obtained through observation of the patient, from any information volunteered by the patient, or through patient questioning.

All AEs (serious and non-serious) which occur from signature of the informed consent through patient participation in the study (last planned visit or early withdrawal date) will be reported and recorded in the eCRF. It is important that the AE dedicated pages of the eCRF includes the duration of the AE (onset/resolution dates), the relationship to the drug, the severity, the outcome, the action(s) taken and relevant concomitant treatments dispensed.

All AEs should be followed-up to determine outcome of the reaction. The Investigator should follow up the event until resolution or stabilization of the condition. It is the Investigator’s responsibility to assure that the subjects experiencing an AE receive definite treatment for any AE, if required.

Medical conditions/diseases present before starting study treatment shall be documented in the medical history section of the eCRF; these conditions are considered AEs only if they increase either in frequency or severity once informed consent has been signed.

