### Relationship of the Adverse Event to the IMP

None (Intercurrent Event)	An event that is not and cannot be related to the Investigational Product, e.g. a surgical intervention for nevus removal performed during the study, but planned before patient enrolment into the study
Unlikely (remote)	Relationship is not likely e.g. a clinical event including laboratory test abnormality with temporal relationship to drug administration which makes a causal relationship improbable and in which other drugs, chemicals or underlying disease provide more plausible explanations
Possible	Relationship may exist, but could have been produced by the patient's condition or treatment or other cause
Probable	Relationship is likely, the AE abates upon discontinuation of Investigational Product and cannot be due to the patient's condition
Highly Probable	Strong relationship, the event abates upon discontinuation of Investigational Product and, if applicable, re-appears upon repeat exposure

Any AE reported in the study having a possible, probable or highly probable relationship to study drug will be considered as an ADR.

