#### 8.3.2. Severity of AEs

The Investigator will grade the severity of any AE using the definitions in the **Table** below. For each episode, the highest severity grade attained should be reported.

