# PPD

For summaries, the drug-event relationship will be assessed as “None”, “Unlikely”, “Possible” “Probable” or “Highly probable”. Any TEAE reported in the study having a possible, probable or highly probable relationship to IMP will be defined as “Adverse Drug Reaction” (ADR).

The following tables and listings will be presented by treatment group:

- An overview of TEAEs including the number of patients who exhibited at least one TEAE, at least one severe TEAE, at least one serious TEAE, at least one non-serious TEAE, at least one ADR, at least one serious ADR, number of TEAEs, number of non-serious TEAEs, number of TESAEs, number of ADRs, number of serious ADRs, number of deaths, number of patients who discontinued IMP due to a TEAE;
- Summary of TEAEs by primary System Organ Class and Preferred Term and by study period (on treatment/follow-up and overall);
- Summary of TEAEs by primary System Organ Class, Preferred Term and Severity;
- Summary of Serious TEAEs by Primary System Organ Class and Preferred Term and by study period (on treatment/follow-up and overall);
- Summary of ADRs by Primary System Organ Class and Preferred Term and by study period (on treatment/follow-up and overall);
- Summary of ADRs by Primary System Organ Class and Preferred Term and Severity;
- Summary of TEAEs leading to IMP Discontinuation by Primary System Organ Class and Preferred Term and by study period (on treatment/follow-up and overall);
- Summary of TEAEs leading to Death by Primary System Organ Class and Preferred Term and by study period (on treatment/follow-up and overall);
- Listing of all AEs by Patient;
- Listing of SAEs by Patient;
- Listing of ADR by Patient;
- Listing of Deaths.

In addition, time-to-event methods will be used to summarize the time to onset of severe hypoglycemic events from first dose of treatment. Kaplan-Meier estimates and plots will be provided with:

- the 95% confidence interval bounds calculated per the method proposed by Greenwood;
- the respective number of patients at risk and Kaplan-Meier estimates at different time points;
- the median and its 95% confidence interval;
- the log-rank test p-value.

Subjects who have discontinued/completed the study without an event will be censored at the date of discontinuation/completion. In case of patients still ongoing and free from event at the time of DB lock, they will be censored at the DB lock date.

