# PPD

## 9.3 Partial date conventions

Table 5: Algorithm for Treatment Emergence of Adverse Events

AE START DATE	AE STOP DATE	RULE for TEAE definition	RULE for "Treatment"/"Follow-up" study period definition for TEAE summaries
Known	Known, Partial or Missing	If AE start date < IMP start date, then not TEAE  If AE start date $\geq$ IMP start date, then TEAE	In case of Treatment Discontinuation:  If start date $>$ Date of last IMP intake, then Follow-up study period for TEAE occurrence.  Otherwise, Treatment study period for TEAE occurrence.  In case of NO Treatment Discontinuation:  If start date $\geq$ Date of "Month 12 visit", then Follow-up study period for TEAE occurrence.  Otherwise, Treatment study period for TEAE occurrence.
Partial, but known components show that it cannot be on or after IMP start date	Known, Partial or Missing	Not TEAE	Not Applicable
Partial, could be on or after IMP start date	Known	If AE stop date < IMP start date, then not TEAE  If AE stop date $\geq$ IMP start date, then TEAE	If TEAE, then Treatment study period for TEAE occurrence.

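### A run-in AE with a complete start date that worsens or becomes serious after first dose, if kept as one record, is left out of all TEAE, serious-TEAE and ADR summaries

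*SAP*

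**What the plan says.** SAP 8.1 sets the rule: "Any AE which starts at or after the first administration of study treatment will be considered a Treatment Emergent Adverse Event (TEAE". It adds: "Pre-treatment AEs will be presented in the listings only". Table 5 (SAP 9.3) turns this into an algorithm. For a known start date, whatever the stop date, it reads: "If AE start date < IMP start date, then not TEAE". The stop date matters only when the start date is missing, or is partial and could fall on or after first dose. In those branches the test is "If AE stop date < IMP start date, then not TEAE", and a missing stop date makes the event a TEAE by assumption. No branch deals with a change in severity or seriousness. Protocol 9.5.4 plans TEAE tables, but the protocol does not define the term.

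On recording, Protocol 8.3 collects AEs from consent. Protocol 8.3.2 says: "For each episode, the highest severity grade attained should be reported". For conditions present before treatment, Protocol 8.3 says: "these conditions are considered AEs only if they increase either in frequency or severity once informed consent has been signed". Protocol 8.2 asks for AEs to be reported for clinically relevant untoward changes in concomitant conditions. Neither document says whether worsening after first dose opens a new record with its own onset date.

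On ADRs, Protocol 8.3.1 says: "Any AE reported in the study having a possible, probable or highly probable relationship to study drug will be considered as an ADR". SAP 8.1 starts its definition from the narrower set: "Any TEAE reported in the study having a possible, probable or highly probable relationship to IMP will be defined as" an ADR.

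**The concern.** A definition of treatment emergence normally covers two things: events that begin on treatment, and earlier events that get worse on treatment. The SAP covers only the first when the start date is complete. The run-in can last up to 100 days (Protocol 3.3), so AEs may well be open at first intake. If one becomes severe or serious after dosing, the tables that readers use to judge safety will not show it.

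Safety is a stated objective. After the early stop of enrolment the whole analysis is descriptive (SAP 4.8), so the safety result is the counts themselves. With few patients, one event classified differently is visible.

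**Working it through.** No figure in the plan needs reproducing. The check applies the rules to test cases and then counts the outputs affected.

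**Test cases.** A run-in AE is still open at first intake, then becomes severe and serious and is judged possibly related.

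| Case | How it is recorded | Rule in Table 5 | Result |
|---|---|---|---|
| A | One record, complete pre-dose start date | Known start date before first dose | Not a TEAE |
| B | One record, partial start date that could be on or after first dose; ongoing or ending after first dose | Stop date decides, or TEAE assumed | TEAE |
| C | One record, start date missing; ongoing or ending after first dose | Stop date decides, or TEAE assumed | TEAE |
| D | Worsening entered as a new AE with a post-dose start date | Known start date on or after first dose | TEAE |

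The clinical course is the same in all four cases. Only the completeness of the date (A against B and C) or the way worsening was entered (A against D) changes the result.

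**Outputs that lose case A (SAP 8.1).**
- All 7 summaries by system organ class and preferred term: TEAEs, TEAEs by severity, serious TEAEs, ADRs, ADRs by severity, TEAEs leading to IMP discontinuation, and TEAEs leading to death.
- 13 − 1 = 12 of the 13 overview items. The exception is the number of deaths, which is not limited to TEAEs.
- The ADR listing, because the SAP's ADR is a subset of TEAEs.

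**Outputs that do not depend on TEAE status.**
- The listings of all AEs, SAEs and deaths (SAP 8.1).
- Laboratory, vital-sign and ECG tables (SAP 8.2 to 8.4).
- The severe-hypoglycemia Kaplan-Meier analysis, which takes its events from the diary forms (SAP 8.1, Table 3).
- Treatment discontinuation criteria (SAP 5.3) and reasons for stopping IMP from the EOT form (SAP 5.5).

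**Exposure to the problem.** 100 days / 7 = 14.3 weeks is a ceiling. The flow chart counts the 100 days from first insulin, whereas AE recording starts at consent.

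**Scale of one event.** In the earlier T1D trial (Protocol 2.4.3), 3 of 50 ladarixin patients (6.0%) and 1 of 26 placebo patients (3.8%) had a TESAE. One ladarixin patient fewer would give 2/50 = 4.0%. This shows how sensitive such counts are. It does not estimate how many events this trial would lose.

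**The case against.** The strongest reply is that the loss is inferred. Protocol 8.3.2 says which grade to report; it does not say that one record must be kept or that the original onset date must stand. Protocol 8.2 and 8.3 can be read so that the worsening is itself a new AE, in which case case D applies and nothing is lost. This stands as a limit: the finding is conditional on single-record entry. It does not remove the gap, because neither document chooses between the two practices and the highest-grade instruction fits one record per episode.

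A reader might infer several stronger things that the documents do not support:

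- **That the event disappears from every safety table, or that Table 5 never looks beyond the start date.** The unaffected outputs and the partial and missing branches show otherwise.
- **That the error always undercounts and favours ladarixin.** The known-date row can only undercount, but the worst-case branches can count unchanged run-in AEs as emergent. A difference between arms would require that the drug aggravates existing events, and nothing in the documents shows this.
- **That the SAP simply contradicts the protocol on ADRs.** Protocol 8.3.1 has the wider definition, but Protocol 2.4.3 itself describes ADRs as treatment-emergent. The protocol is on both sides.
- **That 1 to 5% of patients are affected.** This follows from assuming that 10 to 20% have an open AE at Day 1 and that 10 to 25% of those worsen (0.10 × 0.10 to 0.20 × 0.25). Neither input is in the documents. Applying the result to 75 patients would also ignore the early stop of enrolment.

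**Conclusion.** The point holds in limited form. For complete start dates, onset alone decides TEAE status. A run-in AE that increases in severity or becomes serious after first intake, if kept as a single record, is left out of every TEAE, serious-TEAE and ADR summary. The same ongoing event is counted when its start date is missing, or is partial and could fall on or after first dose, so better data can lead to exclusion. This is a stated rule with a gap, not merely missing detail.

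The size is unknown: there is no count of run-in AEs, of those open at first intake, or of those that worsened. It may be zero if sites entered worsening as new AEs. The by-patient AE and SAE listings limit the harm, but they do not put the events into the counts by arm.

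**What to change.** 1. In SAP 8.1, define a TEAE as an AE that starts on or after first IMP intake, or that starts earlier and increases in severity or becomes serious on or after first intake.
2. Amend the known-start-date row of Table 5 to match. That row also assigns the treatment or follow-up period by start date; for these events it should use the date of worsening.
3. Before the Blind Data Review Meeting (SAP 4.9), list all run-in AEs still open at first intake. Settle there, blinded, those without a date of worsening. SAP 3.4 still has the code broken after the last Month 12 visit, so those who decide must not have access to it.
4. Reconcile the ADR wording across Protocol 8.3.1, Protocol 2.4.3 and SAP 8.1, and state which definition the tables use.

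Two wider changes are best avoided. A run-in AE that has not changed should not become emergent only because it was judged related or IMP was stopped. A blanket worst-case rule for undated worsening could reclassify many unchanged run-in AEs, since the AE items named in Protocol 8.3 do not include a date of worsening.

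The cost is a few lines of SAP text, one programming rule and a short blinded review. A few run-in events that worsened for other reasons will count as TEAEs in both arms.

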# PPD

For summaries, the drug-event relationship will be assessed as “None”, “Unlikely”, “Possible” “Probable” or “Highly probable”. Any TEAE reported in the study having a possible, probable or highly probable relationship to IMP will be defined as “Adverse Drug Reaction” (ADR).

The following tables and listings will be presented by treatment group:

- An overview of TEAEs including the number of patients who exhibited at least one TEAE, at least one severe TEAE, at least one serious TEAE, at least one non-serious TEAE, at least one ADR, at least one serious ADR, number of TEAEs, number of non-serious TEAEs, number of TESAEs, number of ADRs, number of serious ADRs, number of deaths, number of patients who discontinued IMP due to a TEAE;
- Summary of TEAEs by primary System Organ Class and Preferred Term and by study period (on treatment/follow-up and overall);
- Summary of TEAEs by primary System Organ Class, Preferred Term and Severity;
- Summary of Serious TEAEs by Primary System Organ Class and Preferred Term and by study period (on treatment/follow-up and overall);
- Summary of ADRs by Primary System Organ Class and Preferred Term and by study period (on treatment/follow-up and overall);
- Summary of ADRs by Primary System Organ Class and Preferred Term and Severity;
- Summary of TEAEs leading to IMP Discontinuation by Primary System Organ Class and Preferred Term and by study period (on treatment/follow-up and overall);
- Summary of TEAEs leading to Death by Primary System Organ Class and Preferred Term and by study period (on treatment/follow-up and overall);
- Listing of all AEs by Patient;
- Listing of SAEs by Patient;
- Listing of ADR by Patient;
- Listing of Deaths.

In addition, time-to-event methods will be used to summarize the time to onset of severe hypoglycemic events from first dose of treatment. Kaplan-Meier estimates and plots will be provided with:

- the 95% confidence interval bounds calculated per the method proposed by Greenwood;
- the respective number of patients at risk and Kaplan-Meier estimates at different time points;
- the median and its 95% confidence interval;
- the log-rank test p-value.

Subjects who have discontinued/completed the study without an event will be censored at the date of discontinuation/completion. In case of patients still ongoing and free from event at the time of DB lock, they will be censored at the DB lock date.

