### **Procedures**

Potential study patients with a recent clinical diagnosis of T1D with a fasting C-peptide  $\geq$ 0.205 nmol/L on two occasions; these patients will be considered if they fall within the definition of new-onset T1D (randomization scheduled to allow the administration of the study medication to start within 100 days from 1st insulin administration) and will have diagnosis (positive for at least one auto-antibody).

Each patient will be involved in the study for a run-in period (one or more visits) and the randomization visit, followed by a treatment period of 12 months. During treatment, 5 visits will be scheduled at the end of the 3rd (Week 11) and 6th (Week 23) treatment cycles, at Month 6 (Week 26), at the end of the 9th (Week 35) treatment cycles, and at Month 12 (Week 52) after the 1st dose of study treatment. An additional post-treatment visit will be scheduled at Month 18. Study period/visits are summarized in the study flow chart (see [Appendix 14.2](#))

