#### 3.3. OVERALL STUDY DESIGN

The study will be a phase 2, multicenter, double-blind, placebo-controlled study.

It has been designed to evaluate whether ladarixin is effective in preserving  $\beta$ -cell function and slowing-down the progression of T1D in patients maintaining a high residual  $\beta$ -cell function at onset.

It will involve 75 adult (18-45 years, inclusive) patients with new-onset T1D. Patients will be randomly (2:1) assigned to receive either ladarixin treatment (400 mg b.i.d. for 13 cycles of 14 days on/14 days off - treatment group) or matched placebo (control group). The two groups will be balanced within centers.

Recruitment will be competitive among the study sites, until the planned number of patients is enrolled. Competitive recruitment has been chosen to increase the speed of recruitment and to account for any difference among study sites in the rate and timing of patient referral.

Each patient will be involved in the study for a run-in period (Screening and Baseline assessments) followed by a randomization visit and a post-randomization period up to 18 months from the 1st IMP dose, as per details below:

- A run-in period including 2 or more visits up to a maximum of 100 days; this includes the time required to confirm the diagnosis, assess fasting C-peptide, and perform baseline assessment;
- A randomization visit;
- A treatment period of 12 months, to include 5 visits scheduled at the end of the 3rd (Week 11) and 6th (Week 23) treatment cycles, at Month 6 (Week 26), at the end of the 9th (Week 35) treatment cycle and at Month 12 (Week 52) from the 1st dose of study treatment;
- One post-treatment follow-up visits scheduled at Month 18 (week 78) from the 1st dose of study treatment.

[figure not shown]
Figure 1 shows the major milestones of the study design (run-in period, treatment, follow-up visits).

**First treatment administration should start within maximum 100 days from the first insulin dose** and will continue for 3 months. Administration will be extended up to one year only after **the FDA has notified that such longer exposure to ladarixin** is acceptable after having reviewed chronic toxicology data in rats and dogs.

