## 7. STUDY PROCEDURE AND ASSESSMENTS

A schedule for the tests and evaluations to be conducted in this study is found in the flow chart in [Appendix 14.2](#).

For all measurements, the actual date and time of assessment, including date of sampling, will be recorded in the eCRF. Time frame for each assessment is reported in the following sections. Month /Week match is detailed below, together with acceptable windows:

Month 6 = Week 26±2; Month 12 = Week 52±2; Month 18 = Week 78±2.

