### 8.2. MONITORING FOR ADVERSE EVENTS

At each visit following study informed consent form signature, after the subject has had the opportunity to spontaneously mention any problem, the Investigator or appropriate designee should inquire about AEs by asking the standard questions:

- “Have you had any health problems since your last study visit?”
- “Have there been any changes in the medicines you take since your last study visit?”

AEs should be reported for any clinically relevant change in concomitant condition(s) that is the result of an untoward (unfavorable and unintended) change in a subject’s medical health. Changes in any protocol-specific systemic parameter evaluated during the study are to be reviewed by the Investigator. Any untoward (unfavorable and unintended) change in a protocol-specific parameter or questionnaire response that is clinically relevant is to be reported as an AE. These clinically relevant changes will be reported regardless of causality.

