# PPD

## 6. Evaluation of Treatment Compliance and Exposure

### 6.1 Compliance to study treatment regimen

Descriptive analyses of the following parameters will be presented by treatment group for each cycle and during the entire treatment period:

- from IMP dispensation form
  - number of capsules dispensed;
- from IMP accountability form
  - number of returned blisters;
  - number of capsules taken;
  - number of returned unused capsules;
  - IMP intake compliance, ON -treatment period compliance (only by cycle);

Patients are instructed to receive study treatment (either ladarixin or placebo) as follows:

- 400 mg b.i.d (2 capsules at each administration, twice per day);
- for 13 cycles, each lasting 28 days;
- each cycle is composed by 14 consecutive days on-treatment and 14 consecutive days off-treatment.

Calculation of compliance to treatment regimen must consider not only the amount of treatment intake, but also the correct alternation between period “ON” and period “OFF” and their duration. To assess the overall compliance to treatment regimen, the following 3 criteria will be taken into account:

- Compliance to IMP intake;
- Compliance to duration of period “ON” (period of the cycle when the patient is ON treatment);
- Compliance to duration of period “OFF” (period of the cycle when the patient is OFF treatment).

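### SAP 8.1 splits adverse events by study period as crude percentages and counts, with no patient-time or period-specific denominator, so the periods cannot be compared

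*SAP*

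**What the plan says.** SAP 8.1 states that "TEAEs summaries will be presented, displaying frequencies and percentages of patients reporting AEs", and adds the number of events. Five summaries are then divided into on-treatment, follow-up and overall: all TEAEs ("Summary of TEAEs by primary System Organ Class and Preferred Term and by study period (on treatment/follow-up and overall"), serious TEAEs, ADRs, TEAEs leading to IMP discontinuation and TEAEs leading to death. All are presented by treatment arm. SAP Table 2 assigns adverse events to the Safety set, and SAP 4.7 keeps missing values in percentage denominators. Neither place, nor SAP 8.1, mentions patient-time or a denominator for the follow-up column.

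SAP Table 5 sets the boundary between periods. For a patient who does not discontinue, follow-up begins at the Month 12 visit. For one who does, it begins after the last IMP intake. TEAEs whose start date is missing, or is partial and could fall on or after IMP start, go to the treatment period.

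Protocol 3.3 describes the on-treatment schedule as "A treatment period of 12 months, to include 5 visits scheduled at the end of the" third, sixth and ninth cycles and at Months 6 and 12. It then plans "One post-treatment follow-up visits scheduled at Month 18 (week 78". Protocol 8.2 ties the adverse-event question to visits ("At each visit following study informed consent form signature, after the subject has had the opportunity to spontaneously mention any problem").

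**The concern.** A percentage of patients with at least one event, and a count of events, both grow with the time observed. The two period columns cover different lengths of time, and the lengths vary from patient to patient with the date of last intake. A lower figure in follow-up than on treatment can therefore arise with no change in risk, and a reader may take it for a drug effect that resolves. If one arm has more discontinuation, its patients contribute less time to the treatment column and more to follow-up. The arms then differ within each column for a reason unrelated to risk. A patient who never enters follow-up may also be counted there as event-free. Since all analyses are now descriptive (SAP 4.8), these tables will be read directly, with no model that accounts for time.

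**Working it through.** **Period lengths for a patient who completes treatment**
- SAP 6.1 specifies treatment "for 13 cycles, each lasting 28 days": 13 × 28 / 7 = 52 weeks, which matches Month 12 = Week 52.
- Follow-up: 78 − 52 = 26 weeks.
- Protocol 7 gives the windows: "Month 12 = Week 52±2; Month 18 = Week 78±2". Follow-up therefore ranges from 76 − 54 = 22 to 80 − 50 = 30 weeks.
- Scheduled visits: 5 in 52 weeks (one per 10.4 weeks) and 1 in 26 weeks.

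**Period lengths for a patient who stops IMP but stays to Week 78 (SAP Table 5)**

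Stopping points after cycles 3, 6 and 9 are used because Protocol 6.4.2 checks discontinuation criteria then. The last intake of cycle c falls at ((c − 1) × 28 + 14) / 7 weeks.
- Cycle 3: 10 weeks on treatment, 68 in follow-up.
- Cycle 6: 22 and 56.
- Cycle 9: 34 and 44.

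**Effect of length alone**

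Protocol 2.4.3 reports TEAEs in 74.0% (ladarixin) and 84.6% (placebo) in the earlier T1D trial. Two assumptions are made: these are 52-week proportions, and all patients in an arm share one constant rate λ.
- λ = −ln(1 − P) / 52. Ladarixin: 1.347 / 52 = 2.59 per 100 patient-weeks. Placebo: 1.871 / 52 = 3.60.
- Proportion in t weeks = 1 − exp(−λt).
- t = 26: 49.0% and 60.8%. Falls: 74.0 − 49.0 = 25.0 and 84.6 − 60.8 = 23.8 points.
- t = 22 to 30: 43.4 to 54.0% and 54.7 to 66.0%.
- A term seen in 10% over 52 weeks would be seen in 5.1% over 26.
- Expected event counts halve (26 / 52). The rate per patient-time is the same in both periods.

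The 24 to 25 points are a ceiling for this effect. If patients have different constant rates, the 26-week proportion is at least 1 − √(1 − P), which is 49.0% or 60.8%. The fall can then only be smaller.

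**The reverse pattern**

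At the same ladarixin rate, a patient who stops after cycle 3 has probability 22.8% in the 10-week treatment period and 82.8% in the 68-week follow-up.

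**Between arms**

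Take the same rate in both arms. Suppose 10% of one arm stop IMP early and stay in the study, and none in the other. The 10% is an assumption, borrowed from the drop-out allowance in Protocol 9.1.
- Stopping after cycle 3, treatment column: 0.9 × 74.0 + 0.1 × 22.8 = 68.9%, against 74.0%.
- Stopping after cycle 3, follow-up column: 0.9 × 49.0 + 0.1 × 82.8 = 52.4%, against 49.0%.
- Stopping after cycle 9 (58.6% and 68.0%): 72.5% against 74.0%, and 50.9% against 49.0%.

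**Denominator**

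If instead 10% left the study before follow-up and stayed in the denominator, 49.0% would read 0.9 × 49.0 = 44.1%.

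**The case against.** No test between periods is planned, and the trial is descriptive after enrolment stopped early. Both arms follow one schedule, so a fall due to length would show under placebo too. That stands: the comparison of arms within a period is not distorted by this feature unless discontinuation differs by arm, and the documents give no evidence that it does. The table layouts are in mock shells that are not part of the documents, so a denominator may be set there. That is possible, but SAP 5.3 and 5.4 state restricted denominators in the text and SAP 8.1 does not. SAP 6.2 summarises exposure by arm, but its derivation ends at last intake and covers no follow-up time.

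A reader might go further than the documents allow, in four ways.
- **That event rates fall after treatment by construction.** The SAP shows percentages and counts, not rates. A constant rate stays constant, and for early discontinuers the direction of the crude figures reverses.
- **That adverse-event enquiry drops from five occasions to one.** The visit question covers the whole interval since the previous visit. Protocol 8.3 also accepts observed and volunteered events. Protocol 7.1.1 expects telephone contact at least every 2 to 3 weeks throughout participation, although for metabolic control. Less complete capture in follow-up is possible, but its size is unknown.
- **That the period split is the only view of whether events track the drug.** There is a concurrent placebo arm, ADR tables, and a Kaplan-Meier analysis of severe hypoglycaemia.
- **That the spacing of laboratory tests adds to the problem.** SAP 8.2 tabulates laboratory data by visit, not by period.

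**Conclusion.** The point holds as a matter of presentation. Crude percentages and counts in the five period-split summaries are not comparable across periods. They are comparable between arms within a period only if discontinuation is similar. Under the equal-rate assumption and the borrowed 52-week proportions, length alone accounts for a fall of at most about 24 to 25 points in the overall TEAE percentage for completers, and of about half for a rare term. Allocating undated TEAEs to the treatment period pushes completers' results the same way, by an amount that cannot be computed. The size of any between-arm effect depends on discontinuation that the documents do not report. The primary analysis is not affected.

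**What to change.** In SAP 8.1, for each table split by study period, add by arm and period:
- the number of patients who entered the period, used as the percentage denominator;
- patient-years at risk, with start and end dates following Table 5;
- events per 100 patient-years.

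Add a footnote stating the Table 5 rule: the boundary is the Month 12 visit, or the last intake for patients who discontinued. It should say that TEAEs with a missing start date, or a partial one that could fall on or after IMP start, are placed in the treatment period. It should also say that scheduled visits are less frequent in follow-up, while telephone contact continues every 2 to 3 weeks.

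The SAP already uses the dates needed (first and last intake, Month 12 visit, study exit), so no new data are required. The cost is a short change of wording and slightly wider tables.
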